Plasma exposures to TERN-201 were greater than dose proportional. TERN-201 was rapidly cleared from plasma. Steady state was achieved in the highest dose group (10 mg) after Day 7 of dosing. The half-life of TERN-201 increased with dose, suggesting saturable, target-mediated clearance.

Single and multiple doses of TERN-201 significantly suppressed plasma total amine oxidase activity at all doses studied. Using an exploratory assay to assess the effect of TERN-201 on VAP-1/SSAO-specific amine oxidase activity in the plasma, near complete inhibition (>80% with 1 mg, > 90% with 10 mg) was observed after only a single dose on Day 1 (achieved within 4 hours after dosing) with sustained suppression over the dosing period in MAD cohorts. Dose-dependent increases in methylamine, an endogenous substrate of VAP-1/SSAO predicted to increase upon VAP-1/SSAO inhibition, were observed after the first dose of TERN-201 and continued to increase in a dose-dependent manner after multiple doses of TERN-201.

Based on the exploratory assessment on plasma PK of two TERN-201 metabolites, TRN-001021 and TRN-001744, the percentages of either metabolite AUC relative to the total TERN-201-related plasma AUC (sum of TERN-201, TRN-001021, and TRN-001744) were calculated. Median TRN-001021 AUC was <10% and 13.7% of the total plasma AUC associated with TERN-201 in the 4 mg and 10 mg groups, respectively. Median TRN-001744 AUC was 11.5% and <10% of the total plasma AUC associated with TERN-201 in the 4 mg and 10 mg groups, respectively.

Additional details on Study TERN201-US-A101 are available in the Investigator's Brochure.

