4.3. Justification for Dose

Doses for this study were based on results from the FIH Phase 1 study, TERN201-US-A101, which evaluated 4 SAD cohorts of TERN-201 or matching placebo at 1 mg, 3 mg, 6 mg, or 10 mg, and 3 MAD cohorts of TERN-201 or matching placebo at 1 mg for 7 days, 4 mg for 7 days, or 10 mg for 14 days.

In the FIH study, single or multiple doses of TERN-201 resulted in rapid inhibition of plasma amine oxidase activity, with sustained inhibition during 14 days of dosing. TERN-201 demonstrated a favorable safety profile and was overall well-tolerated at all doses studied (Section 2.2.2).

Part 1 of this study assesses 10 mg of TERN-201, the highest dose studied in the FIH study. In the FIH study, this dose led to >90% suppression of plasma VAP-1/SSAO-specific amine oxidase activity in healthy participants. NASH patients are expected to have a higher baseline level of VAP-1, and thus the PD effect of TERN-201 in NASH patients may differ from healthy participants. A higher dose of up to 20 mg may be enrolled based on assessment of safety and PK with the 10 mg dose, and a lower dose of 4 mg may be enrolled based on observation of a robust PD effect of TERN-201 on plasma VAP-1/SSAO activity in the 10 mg cohort, thus minimizing the number of patients exposed until the PK and PD effects of TERN-201 can be confirmed in Part 1 of the study.

Toxicity and safety pharmacology studies support starting with the 10 mg dose and enrolling a higher dose up to 20 mg.

Additional details on available data from Study TERN201-US-A101 are provided in the TERN-201 Investigator's Brochure.

5. Study Population

Prospective approval of protocol deviations to recruitment and enrollment criteria, also known as protocol waivers or exemptions, is not permitted.

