#### **8.8.4.3. Statistical Methods for PD Parameters**

Plasma PD parameters will be summarized by treatment group using descriptive statistics (number of non-missing observations, arithmetic mean, SD, median, Q1, Q3, minimum, maximum, geometric mean, and geometric CV%).

For the calculation of summary statistics, all NR and not calculated (NC) values in a data series will be set to missing.

Analyses of pre-dose/trough values for plasma VAP-1/SSAO activity ( $A_{avg}$  and  $A_{min}$ ) and methylamine ( $C_{avg}$  and  $C_{max}$ ) at Week 0/Day 1, Week 6, and Week 12 will be carried out using an ANCOVA model with the PD parameter as the dependent variable including treatment group as a fixed effect and baseline VAP-1/SSAO activity or methylamine concentration as a covariate. The model will be carried out separately for the PD parameter based on the VAP-1/SSAO activity and methylamine value, change from baseline, and percent change from baseline. The estimates of LS means, SE, and 90% and 95% CIs will be presented by treatment group. Estimates of the LS mean difference for each pairwise comparison will be presented with associated the standard error of the difference, and 90% and 95% CIs of the difference.

The distribution of parameter values will be evaluated visually for normality assumptions. If normality assumptions are violated, first the data will be natural log transformed and the log transformed data evaluated for normality. If the log transformed data are normally distributed, the same ANOVA model described above will be used.

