### 8.9. Exposure Response Analyses

The plasma PK parameters  $AUC_{tau}$ ,  $C_{max}$ , and  $C_{tau}$  will be used to evaluate exposure-response. PK parameters will be set to 0 for the placebo group for the purpose of PK/PD.

Pharmacodynamic exposure-response analyses of plasma VAP-1/SSAO activity and methylamine concentration PD parameters will be performed using several exposure-response models for the PK/PD Analysis Set, including but not limited to linear, quadratic, exponential, and  $E_{max}$ . The best fit significant model will be chosen based on AIC, the smaller the AIC value the better the model fit.

Additional exposure-response and dose-response (as applicable) analyses may be explored for baseline patient characteristics such as sVAP-1, BMI, diabetes mellitus, or other characteristics or additional efficacy, safety, and PD endpoints, as needed. These analyses will be described in a separate document.

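### SAP 8.9 leaves baseline out of its exposure-response models and does not say which PD scale they use, so slopes on raw activity or absolute change may partly reflect baseline target level

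*SAP*

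**What the plan says.** SAP 8.9 relates three exposure measures (AUCtau, Cmax, Ctau) to the VAP-1/SSAO and methylamine PD parameters. The analyses "will be performed using several exposure-response models for the PK/PD Analysis Set, including but not limited to linear, quadratic, exponential" and Emax. Model choice is by fit: "The best fit significant model will be chosen based on AIC, the smaller the AIC value the better the model fit". For placebo, "PK parameters will be set to 0 for the placebo group for the purpose of PK/PD". No covariate is named.

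Baseline sVAP-1 does appear in the section, but only as something that "may be explored for baseline patient characteristics such as sVAP-1, BMI, diabetes mellitus, or other characteristics", followed by "These analyses will be described in a separate document".

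Elsewhere the SAP adjusts the same markers for baseline. The ANCOVA for PD parameters in 8.8.4.3 has "treatment group as a fixed effect and baseline VAP-1/SSAO activity or methylamine concentration as a covariate", and it keeps that covariate when the outcome is change or percent change. The ANCOVA in 8.8.3 and the dose-response MMRM in 8.8.4.4 also carry baseline. SAP 8.1 requires baseline for ANCOVA and MMRM comparisons of treatment groups, which does not reach the models in 8.9.

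Tables 8 and 9 derive most PD parameters three ways: value, change and percent change. SAP 8.9 does not choose among them. The secondary endpoint in SAP 2.3.2 is percent change.

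On mechanism, Protocol 2.2.2 says of the first-in-human study: "The half-life of TERN-201 increased with dose, suggesting saturable, target-mediated clearance". Protocol 4.3 adds: "NASH patients are expected to have a higher baseline level of VAP-1, and thus the PD effect of TERN-201 in NASH patients may differ".

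**The concern.** In the ANCOVA and MMRM, treatment group is randomized, so baseline mainly adds precision. Exposure within a dose group is not randomized. In Part 1 there is one active dose, so all exposure variation among treated patients is of this non-randomized kind.

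If clearance depends on the amount of target, a patient with more VAP-1 would tend to have lower exposure. The same patient would also start from higher activity and keep more of it at the same fractional inhibition. Baseline would then produce an association between exposure and residual activity with no effect of exposure itself. Because 8.9 reports the best-fitting significant model, such an association could become the reported exposure-response result. Exposure-response is a listed exploratory endpoint (SAP 2.3.3), so its interpretation is what is at stake.

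**Working it through.** The plan states no power, error rate or effect size for this analysis, so there is no figure to reproduce. The steps below show the direction of the bias, then its possible size.

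**Inputs from the documents.** Sub-study patients on active drug: about 8 in Part 1 and about 6 per dose in Part 2 (SAP 2.2), so 6 + 8 + 6 = 20 over three doses. Protocol 6.4 gives 6 rather than 8 for Part 1; the other sections give 8. Two-sided 5% level (SAP 4.1).

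**Assumptions, none in the documents.** Baseline log-normal with CV about 40%; exposure CV about 50% within dose; correlation rho of baseline with log exposure -0.5 to -0.7; residual activity 8% of baseline (compatible with the more than 90% suppression in Protocol 2.2.2); log-scale noise SD 0.2 to 0.5; no true exposure effect.

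**Step 1: sign by scale.** Let B be baseline, A residual activity and X exposure. With constant fractional inhibition, A = 0.08 B apart from noise.
- Value: cov(A, X) = 0.08 cov(B, X). This is negative when cov(B, X) is negative, so more exposure looks better.
- Change: A - B = -0.92 B, so cov(A - B, X) = -0.92 cov(B, X). This is positive, so more exposure looks worse.
- Percent change: 100 (A - B)/B = -92 for everyone, so there is no slope.

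The spurious slope on change is 0.92/0.08 = 11.5 times that on value, with opposite sign.

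**Step 2: effect of adding baseline.** A - B = a + bX + cB is the same equation as A = a + bX + (c + 1)B. Once baseline is in a linear model, value and change give the same exposure slope b and the same test, so the contradiction in Step 1 disappears.

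**Step 3: size.** Generator: log exposure = 1.3 ln(dose/10) + 0.47 [rho z + sqrt(1 - rho²) e]; log baseline = 0.39 z; log activity = 0.39 z + ln(0.08) + noise. A linear model of the outcome on exposure, in treated patients only, rejects a true null this often:

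| Outcome | 8 treated | 20 treated |
|---|---|---|
| Value, no baseline term | 7-30% | 5-18% |
| Change, no baseline term | 18-43% | 11-24% |
| Percent change, no baseline term | 4-6% | 4-6% |
| Value or change, baseline included | about 2-4% across both sizes | |

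A repeat with 3,000 runs per setting agreed to within about one percentage point.

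**Step 4: a different generator.** Here a share f of clearance is proportional to baseline target. For f = 0.3 to 0.9 with no baseline term, 8 treated patients give 15-49% (value), 15-68% (change) and 4-5% (percent change). Twenty treated give 6-31%, 8-43% and 4-5%. With f = 0 every rate is about 5%. With baseline included, rates are 2-6%.

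**Step 5: Emax fit with placebo at zero exposure.** With 27 patients, percent change and a true EC50 of 2.0, the unadjusted median EC50 stays near 2.0 if EC50 does not depend on baseline. If EC50 is proportional to baseline, it rises to 2.2-2.6 for f = 0.3 to 0.9, an overstatement of about 10-30%.

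**Step 6: precision.** If baseline explains 25% of outcome variance (correlation 0.5, assumed), adjustment multiplies the slope variance by 0.75/(1 - rho²). Start from 60% power, noncentrality 2.213:
- rho = 0: factor 0.75; 2.213/sqrt(0.75) = 2.556; power = Phi(2.556 - 1.960) = 72%.
- rho = -0.5: factor 0.75/0.75 = 1; power stays at 60%.
- rho = -0.7: factor 0.75/0.51 = 1.47; 2.213/sqrt(1.47) = 1.825; power = Phi(-0.135) = 45%.

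**The case against.** The strongest reply is about scale. The secondary endpoint is percent change, and on that scale the unadjusted models hold their level. This stands, on the condition that fractional inhibition does not depend on baseline. It does not close the point, because 8.9 never says that percent change is what it models. The condition can also fail. EC50 may rise with baseline (Step 5). Or most post-dose values may be below quantification and set to half the limit (SAP 8.8.1), so that percent change becomes a function of baseline.

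Four stronger readings are tempting, and the documents do not support them.
- A reader might take baseline target level as an established common cause of exposure and response. Protocol 2.2.2 only suggests target-mediated clearance, from half-life across doses in healthy participants. Protocol 4.3 compares NASH patients with healthy participants and says nothing about exposure among NASH patients. No correlation is given.
- A reader might say that sVAP-1 is left out. It is named in 8.9, as optional and deferred. The model list is also open-ended, which permits covariates without prespecifying any.
- A reader might expect a power gain from adjustment. Step 6 shows that the gain needs baseline and exposure to be nearly uncorrelated, which is the case without confounding.
- A reader might infer that 8.9 decides dose. Part 2 dosing rests on interim suppression, PK, exposure limits and safety (SAP 8.3, Protocol 9.5). Testing is nominal and exploratory (SAP 8.6).

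The rates in Step 3 also describe slopes among treated patients only. With placebo entered at zero exposure, the real drug-placebo difference contributes to the slope, so these are not error rates of the full analysis in 8.9.

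**Conclusion.** The concern holds in a limited form. SAP 8.9 does not fix the PD scale and prespecifies no baseline adjustment, unlike the SAP's other models for the same markers. On raw value or absolute change, a spurious exposure slope is plausible, and the two scales could point in opposite directions. Under the assumed correlations, false positives run from about nominal to 30% on value and from 11% to 43% on change; adding baseline removes the excess. On percent change there is no inflation while fractional inhibition is independent of baseline.

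The sizes rest on correlations and variances that the documents do not give. They show what could happen and do not estimate what will. Severity is minor: the analysis is exploratory and the sub-study is small.

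**What to change.** Amend SAP 8.9 to:
1. State the PD scale, with percent change from baseline as the main one.
2. Add baseline VAP-1/SSAO activity as a covariate in each model, or baseline methylamine for methylamine outcomes. For Emax on the raw value, put baseline on E0, with the drug effect expressed as a fraction of E0. For Emax on percent change, say which parameter carries baseline.
3. Report adjusted and unadjusted exposure slopes side by side among TERN-201 patients.
4. Prespecify one sensitivity model with baseline sVAP-1 in place of baseline activity, using one covariate at a time.

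The cost is SAP wording and one degree of freedom; both baselines are already collected pre-dose on Day 1. The downside is a wider interval for the slope if baseline and exposure are correlated. Before any credit for lower residual variance, the standard error grows by sqrt(1/0.75) = 1.15 at rho = -0.5 and by sqrt(1/0.51) = 1.40 at rho = -0.7. The case for the change is interpretability; it should not be presented as a gain in power.

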## **8.10. Exploratory Efficacy Analyses**

### **8.10.1. Magnetic Resonance Imaging**

MRIs will be evaluated by a central reader. The following analyses of MRI will use the Efficacy Analysis Set. Sensitivity analyses using the PP and Treatment Completer Analysis Sets will be presented if the analysis set differs from the Efficacy Analysis Set by more than 10% total.

#### **8.10.1.1. Corrected T1 (cT1)**

cT1 related to the amount of extracellular fluid present in the liver parenchyma. cT1 is derived from T1 and T2\* maps. T1 is a measure of the longitudinal (spin-lattice) relaxation time, measured in milliseconds (msec), of a given substance. The T1 of a tissue depends on its free water content, which relates to the proportion of the extracellular fluid in the tissue.

Proton-dense tissues with a low water content, such as fat, have very short T1 values, while tissues with a high water content, such as muscle and the spleen have much longer T1 values. When tissue is inflamed or scarred (fibrotic), changes in the structural organization of the tissue, due to tissue remodeling, mean that the water content increases, leading to longer T1 values.

cT1 is measured in milliseconds (msec). The cT1 metric is calculated from all pixels with whole slice ROIs placed on the cT1 parametric map. The cT1 metric is displayed as a median and IQR, the median will be used in all analyses.

Analyses of cT1 will be based on the Efficacy Analysis Set. Descriptive statistics of the cT1 values, change from baseline, and percent change will be summarized by treatment group and visit.

Analyses of change (and separately percent change) from baseline will be carried out using an ANCOVA model at each scheduled visit with change (and separately percent change) from baseline as the dependent variable including treatment group and randomization strata as fixed effects and baseline as a covariate.

The estimates of least-square (LS) means, standard errors (SE), and 90% and 95% CIs will be presented by treatment group. Estimates of the LS mean difference for each pairwise comparison will be presented with associated the standard error of the difference, and 90% and 95% CIs of the difference.

The primary analysis of change (and separately percent change) at Week 12 will be carried out using available observed data only, without imputation for missing data. The same ANCOVA

model will be used to present the last on treatment value for Week 12, to be labelled as “Week 12/End of Treatment”. For patients who complete Week 12, the Week 12 value will be used. For patients who do not complete treatment, the last value on treatment will be used.

The distribution of change (percent change) values will be evaluated visually for normality assumptions. If normality assumptions are violated, first the data will be natural log transformed and the log transformed data evaluated for normality. If the data are not normally distributed, a Wilcoxon Rank Sum Test will be used to compare treatment groups. The median differences and 90% and 95% CIs of the median differences between treatment groups will be constructed using Hodges-Lehmann estimate.

Sensitivity analyses using the PP and Treatment Completer Analysis Sets will be presented if the analysis set differs from the Efficacy Analysis Set by more than 10% total.

cT1 will be categorized as low (<800 msec), elevated (800 – 900 msec), and high (>900 msec). A shift table from baseline to Week 6 and baseline to Week 12 will be presented by treatment group.

In addition, cT1 responders will be defined as any patient with a decrease of at least 80 msec. Non-responders will be defined as any patient who did not have at least an 80 msec decrease. For both endpoints, the number and percentage, with associated two-sided exact (Clopper-Pearson) 90 and 95% CIs, of patients in each category will be presented by treatment group at each post-baseline visit. A Chi-square test at each post-baseline visit will be used to compare each pairwise comparison between placebo and each active dose of TERN-201.

The number and percentage of patients who are responders on cT1 and ALT will be summarized and analyzed in the same manner as responders.

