#### 4.5. Standard Calculations

Variables requiring calculation will be derived using the following formulas:

- Days – A duration expressed in days between one date (*date1*) and another later date (*date2*) will be calculated using the following formulas:
  - duration in days =  $date2 - date1 + 1$ , where  $date1 \geq$  first administration date
  - duration in days =  $date2 - date1$ , where  $date1 <$  first administration date
- Months – A duration expressed in months is calculated as the number of days divided by 30.4375
- Years – A duration expressed in years between one date (*date1*) and another date (*date2*) is calculated using the following formulas:
  - duration in years =  $(date2 - date1 + 1)/365.25$ , where  $date1 \geq$  first administration date
  - duration in years =  $(date2 - date1)/365.25$ , where  $date1 <$  first administration date
- Body Mass Index (BMI) – BMI is calculated using height (cm) and weight (kg) using the following formula:
$$BMI \text{ (kg/m}^2\text{)} = \text{weight (kg)} / ([\text{height (cm)} / 100]^2)$$

- Change (CHG; equivalent to absolute change for liver fat content [LFC]) – Change will be calculated as:

Change = later value – earlier (i.e., baseline) value

- Percent change (PCHG; equivalent to relative change for LFC) – Percent change will be calculated as:

Percent change = ([Change] / earlier [i.e., baseline] value) × 100

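### Normality is judged by eye on change values, not on ANCOVA residuals, so a valid ANCOVA can give way to a Wilcoxon test without baseline or stratum

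*SAP*

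**What the plan says.** SAP 8.10.1.1 (cT1) analyses change and percent change at each visit by ANCOVA, "including treatment group and randomization strata as fixed effects and baseline as a covariate". The check that follows is on the outcome: "The distribution of change (percent change) values will be evaluated visually for normality assumptions". Three steps then apply.

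- Log step: "If normality assumptions are violated, first the data will be natural log transformed and the log transformed data evaluated for normality".
- Rank step: "If the data are not normally distributed, a Wilcoxon Rank Sum Test will be used to compare treatment groups".
- Estimate: median differences and intervals "between treatment groups will be constructed using Hodges-Lehmann estimate".

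Neither the Wilcoxon test nor the Hodges-Lehmann interval is given a covariate or a stratum. Residuals are not mentioned. No visual criterion is stated, nor whether arms are pooled for the check.

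The rule reaches 8.10.1.2 (PDFF), 8.10.2 (elastography), 8.10.3 (AST, ALT, GGT) and 8.10.4 (NASH/fibrosis biomarkers) by cross-reference. Through 8.10.4 it also reaches 8.10.5 (inflammation), 8.10.6 (proteinuria) and weight in 8.10.7.

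SAP 8.8.4.3 has a parallel check for the PD parameters: "The distribution of parameter values will be evaluated visually for normality assumptions".

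**The concern.** The normality assumption of an ANCOVA concerns what is left after treatment, stratum and baseline are fitted. Raw change also contains the part that baseline explains. Patients with high starting values tend to fall further, so a right-skewed baseline gives change a long left tail even when the model errors are normal. Skewed baselines are plausible here: several endpoints are enzymes or biomarkers, and cT1 has an entry floor of 800 ms.

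The check can therefore fail because of the feature that the covariate was included to handle, and the remedy then removes that covariate. Precision is lost in arms of 10 to 20 patients. Because the ANCOVA is run visit by visit and the check has no criterion, one endpoint could also be reported by different methods at different visits.

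**Working it through.** The documents give no SD, effect size or power for these endpoints (SAP 3), so there is no planned figure to reproduce. What follows is illustration, and every distribution in it is assumed.

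**Inputs from the SAP**
- Part 1 arms: 20 v 10 (2.2).
- One dose v pooled placebo if Part 2 enrolls: 20 v (10 + 10) = 20 v 20 (4.6).
- Two-sided 0.05 (4.1).
- "Change = later value – earlier (i.e., baseline) value" (4.5), so a decrease is negative.

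**Assumptions**
- Baseline B is log-normal with mean 1 and CV 40–80%.
- Change = −0.5 × (B − 1) + treatment effect + e, with e exactly normal and SD s = 20–30% of the mean. The ANCOVA is therefore correct by construction.
- Shapiro-Wilk p < 0.05 stands in for the visual check.

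**Step 1. How much of raw change comes from baseline.** Within an arm, var(change) / var(residual) = 1 + 0.25 × CV² / s².

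| CV | s | Ratio | One error SD, in SDs of change |
|---|---|---|---|
| 40% | 30% | 1 + 0.04/0.09 = 1.44 | 1/√1.44 = 0.83 |
| 40% | 20% | 1 + 0.04/0.04 = 2.00 | 0.71 |
| 80% | 30% | 1 + 0.16/0.09 = 2.78 | 0.60 |
| 80% | 20% | 1 + 0.16/0.04 = 5.00 | 0.45 |

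The excess over 1 comes from the skewed baseline. A check on raw change sees it, and an unadjusted test carries it as noise.

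**Step 2. How often each check fails (simulation).**

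| Arms | Raw change flagged | Residuals flagged |
|---|---|---|
| 20 v 10 | about 8–56% | about 5% |
| 20 v 20 | about 8–71% | about 5% |

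The low end is CV 40% with s 30%; the high end is CV 80% with s 20%. A separate run with an exponential baseline of SD 1 and error SD 1, without drug effect, gave 5% at slope 0, 8% at slope 0.5, 23–28% at slope 1 and 41–53% at slope 1.5. The effect disappears when change does not depend on baseline.

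**Step 3. The log step.** If it means logging change values, it is undefined for any zero or negative change. At least one such value occurred in over 99% of simulated trials.

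**Step 4. Cost when the ANCOVA was valid** (effect of one error SD, same data as Step 2).

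| Arms | ANCOVA power | Wilcoxon power | Difference |
|---|---|---|---|
| 20 v 10 | about 70% | 26–51% | 19–44 points |
| 20 v 20 | about 86% | 40–72% | 14–46 points |

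In the exponential-baseline run the two tests had equal power at slope 0 and moved apart as the slope grew.

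**Step 5. Cost when a rank method is warranted** (log-normal outcome, CV 60%, log effect −0.35, baseline correlation 0.4 / 0.6 / 0.8).

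| Arms | Wilcoxon on change | Rank ANCOVA | Difference |
|---|---|---|---|
| 20 v 10 | 24 / 31 / 51% | 37 / 45 / 63% | 13 / 14 / 12 points |
| 20 v 20 | 33 / 45 / 71% | 54 / 63 / 84% | 21 / 18 / 13 points |

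Type I error was near 5% for all methods.

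**The case against.** Four points on the other side carry weight.

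- **The switch is not automatic.** The check is visual and has no criterion, so a statistician who sees baseline-driven skew may leave the ANCOVA in place. This stands. The flag rates show direction and range, not the probability of a switch, and they depend strongly on the assumed error SD. The powers in Steps 4 and 5 are conditional on having switched; an overall loss cannot be given.
- **Transformation may intervene.** SAP 4.4 allows a log transformation of variables whose non-normality affects the analysis. If 8.10.1.1 means logging the measurements and not the changes, the Wilcoxon step may be avoided. The SAP does not say which is meant.
- **A second analysis may exist.** If Part 2 enrolls, 8.10.8 applies a baseline-adjusted MMRM with no normality switch to ALT, AST, GGT, cT1, PDFF, CK-18, PRO-C3, C3M and the PRO-C3/C3M ratio. It does not cover the other endpoints, and it is not planned if only Part 1 is run.
- **The analyses are exploratory.** Testing is nominal and unadjusted (8.6), and the Wilcoxon test keeps its size. This limits the priority.

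A reader might also infer that TERN-201's own effect on VAP-1/SSAO would force the switch to Wilcoxon. The documents do not support that. Section 8.8.4.3 has no Wilcoxon step, and its ANCOVA has no stratum to drop. Section 8.8.3, which does model VAP-1/SSAO change with the strata, has no normality check. What remains in 8.8.4.3 is the trigger. With an assumed percent change of −90 v 0 (SD 10–15) in sub-study arms of 8 v 4, pooled raw values were flagged in about 72–99% of trials. That holds only if arms are pooled for the check, which the SAP neither states nor excludes. For the endpoints in 8.10, an effect of one error SD did not raise the flag rate.

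**Conclusion.** The point holds for 8.10.1.1 and the sections that refer to it. The check is on the wrong quantity, and the last fallback discards the baseline and stratum of the planned model. When change depends on a skewed baseline, a valid ANCOVA can be set aside. Under the assumed data the price is 14 to 46 power points against ANCOVA, or 12 to 21 points against a rank method that keeps baseline.

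These sizes rest on assumed distributions, a slope of 0.5 and a formal test in place of a visual one. They do not show that a switch will happen, and they do not show false positives. The harm is lost precision and possibly inconsistent methods across visits in exploratory, nominal analyses. For 8.8.4.3 the point is confined to what is inspected. Priority: low to moderate.

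**What to change.** - In 8.10.1.1 and 8.8.4.3, assess normality on the residuals of the planned ANCOVA.
- In 8.10.1.1, replace the unadjusted Wilcoxon test with rank ANCOVA: outcome rank adjusted for baseline rank, stratified by Screening cT1 (≤ 900 v > 900 ms).
- Keep the Hodges-Lehmann estimate and its intervals as a descriptive companion.
- Use one method per endpoint across visits.
- State whether the log step applies to the measurements or to the changes.

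The cost is SAP wording and a little programming; no new data are needed. The downside is that rank ANCOVA gives a test but no effect estimate on the original scale. The Hodges-Lehmann companion supplies one, but it is unadjusted and need not agree with the test.
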